Is a 6-item self-report instrument that measures treatment credibility, and client expectancy for improvement. The CEQ has high internal consistency ( $\alpha = 0.79-0.90$ ). Retest reliability is  $r = 0.82$  for the expectancy factor and  $r = 0.75$  for the credibility factor (Devilly & Borkovec, 2000). The first four items are rated based on cognitive appraisal of the treatment (e.g. At this point, how successfully do you think this treatment will be in reducing your symptoms?), whereas the last two items are rated based on feelings about the treatment. To reduce demand characteristics, client forms will be sealed in an envelope upon completion, and clients will be told that the therapist will only see the forms after they have finished participation.

*Client Satisfaction Questionnaire (CSQ-8) (Larsen et al., 1979)*

An eight-item version, to evaluate patient satisfaction. The sum of the responses to the CSQ-8 ranges from 8 to 32, with higher scores indicating greater satisfaction. The CSQ-8 has demonstrated high internal consistency across a large number of studies (Attkisson & Greenfield, 1999).

## 12.3 Procedures for Assessing Efficacy Parameters

N/A

## 13. Assessment of Safety

### 13.1 Burden

The burden placed on participants has been minimised as much as possible by carefully considering the inclusion of each measure in the case series. Furthermore, the assessment session can be split into several shorter sessions, should the participant wish. Breaks will be offered in each therapeutic and assessment session and the research therapist will support the participant to ensure that the delivery of the research and therapeutic procedures is acceptable to them and modify if needed. For example, participants will complete daily ratings about their memory via text, email, or phone. The research therapist will discuss with participants how many ratings (up to a maximum of four a day) they are able to complete, and how they would like to be prompted to answer them. This will be reviewed throughout the project.

The electronic version of this document is the latest version. It is responsibility of the individual to ensure that any paper material is the current version. Printed material is uncontrolled documentation.

### **13.2 Risk of Distress**

The focus of this project is distressing, traumatic memories, and participants will be required to focus on and discuss them during their participation which may be difficult. However, there is robust evidence to suggest that trauma-focused therapies can be safely applied in psychosis and that imagery rescripting can be used with this group to reduce distress associated with images (Ison et al., 2014; van den Berg et al., 2016). Participants will be selected as they regularly experience intrusive trauma memories, and therefore the study will only focus on eliciting experiences which they already have. Further, the project supervisors have extensive experience of working with traumatic memories in psychosis and will be able to ensure the intervention is delivered safely and sensitively. Participants will be giving informed consent to participate in the study.

Should the participant become distressed at any point and feel unable to continue with the therapy, then the study will be terminated, and the research therapist will discuss this with them. The supervisors of this project have extensive clinical experience in this group and will be available for consultation should this situation arise. In addition, the research therapist has experience working with this group of people and will manage the situation should it arise with the support of the supervisors. Information pertaining to risk will be shared as needed with the clinical team, in accordance with local risk management protocols. Coping strategies will be discussed with participants at the beginning of the intervention to support them in managing any distress that arises.

### **13.3 Specification, Timing and Recording of Safety Parameters.**

N/A

### **13.4 Procedures for Recording and Reporting Adverse Events**

Safety and adverse event assessment and monitoring: It is an important subsidiary goal of the case series to establish the safety of the intervention, and we will also take all appropriate steps during the conduct of the case series for ensuring participant safety. The occurrence of adverse events (AEs) will be monitored actively and systematically. AEs are defined as including deaths; self-harm; serious violent incidents; complaints about therapy; referrals to crisis care or admission to psychiatric hospital during therapy. A standard method of reporting will be employed, categorising events by severity (five grades, A-E). Investigators will also determine relatedness of an event to the intervention based on a temporal relationship, as well as whether the event is unexpected or unexplained given the participant's clinical course, previous conditions and history, and concomitant treatments, in five categories from 'not related' to 'related' (following Linden 2013). The following will be considered as serious adverse events (SAE, Categories A-C): All deaths (category A), incidents which acutely jeopardise the health or psychological wellbeing of the individual, resulting in immediate hospital admission and/or permanent disability (category B), or resulting in injury requiring immediate medical attention (category C). These SAEs will include but are not limited to: 1) Hospital admissions; 2) Home treatment team involvement; 3) Suicide attempts; 4) Any violent incident necessitating police involvement (whether victim or accused); 5) Self-harming behaviour; 6) All deaths. Reasons for withdrawal from the study will also be recorded. Furthermore, in the event of any AEs and participant withdrawal, the research therapist will review participant clinical notes and contact clinicians for any important additional information. For the final reports of the case series, the numbers, types and severity of AEs, as well as discontinuations, will be reported, using descriptive statistics.

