### 7.3 Trial Flowchart

	Recruitment visit	Assessment visit	Waitlist 1-3 weeks	Treatment period 3 weeks	Week 1 post treatment	1-week appointment post-treatment	Week 2 post-treatment
Patient information	X						
Informed consent		X					
30-minute Semi-structured interview		X					
Psychotic Symptom Rating Scale (PSYRATS)		X					
The Warwick-Edinburgh Mental Well-Being Scale (WEMWBS)		x				x	
The Posttraumatic Diagnostic Scale for DSM-5 (PDS-5)		x				x	
Mini-Trauma and Life Events Checklist (mini-TALE)		x					
Credibility and Expectancy				x			

The electronic version of this document is the latest version. It is responsibility of the individual to ensure that any paper material is the current version. Printed material is uncontrolled documentation.

Questionnaire (CEQ)							
Client Satisfaction Questionnaire (CSQ-8)						x	
Daily trauma index memory dimensions			x		x		x
Imagery Rescripting				x			

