### 8.2 Frequency and duration of intervention

Three weekly sessions of imagery rescripting will be delivered. Sessions will last approximately one hour, and no longer than 90 minutes.

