#### **10.4 Randomisation Procedure / Code Break**

Participants will be randomised to a waitlist time of 1, 2, or 3 weeks. Randomisation will occur at assessment using a computer program.

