**Imagery Rescripting (ImRs):** Participants will receive three sessions of Imagery Rescripting. The first session will include educating the participant about the rescripting protocol, recapping the identified memory, practicing the protocol on a non-threatening memory, and discussing coping strategies. Measures of how well they expect the therapy to work will also be taken at this first ImRs session (Credibility and Expectancy Questionnaire, CEQ). To ensure there are no researcher effects to this measure, participants will rate confidentially and put their answer into an envelope that will not be opened until the participant has completed the study.

The next two sessions will include using imagination to change the trauma memory and problem-solving any problems that occur. Once a 'rescript' the participant is satisfied with is identified, it will then be practiced repeatedly and adapted if necessary. Sessions will last approximately one hour, and no longer than 90 minutes. Participants will continue daily measures during this time.

**Post-intervention follow-up:** Participants will continue to complete daily measures about the memory for two weeks. During this time, at the end of the first week, participants will be asked to meet with the research therapist to assess their posttraumatic stress disorder symptoms (PDS-5), their level of wellbeing (WEBWMS), and how satisfied they were with the intervention (Client Satisfaction Questionnaire, CSQ-8).

This concludes the participant's involvement in the research.

Overall, participation will last a minimum of six and a maximum of eight weeks. During this time, participants will meet with the research therapist five times. That includes three times for therapy and twice to answer questions. The research therapist will also be contacting participants every day to answer four questions, either over the phone, by text or email.

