#### **13.4.1 Adverse events that do not require reporting**

There are no AEs or SAEs that will not be reported for the case series. The period for reporting will commence when participants provide informed consent and continue until the final follow-up questions are completed.

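### The therapy-only limit in the 13.4 adverse event definition contradicts the SAE list and the 13.4.1 reporting window, leaving some crisis referrals ambiguous; the only notes review described follows an event or withdrawal

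*Combined protocol and SAP*

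**What the plan says.** Section 13.4 makes establishing safety a subsidiary goal and promises active, systematic monitoring. Its adverse event definition is an open list: deaths, self-harm, serious violence, complaints about therapy, and "referrals to crisis care or admission to psychiatric hospital during therapy". The same section then lists SAEs, also as an open list. These include hospital admissions, home treatment team involvement, suicide attempts, violence involving the police, self-harm and deaths, with no limit to any phase.

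Section 13.4.1 exempts no AE or SAE from reporting and sets the window: "The period for reporting will commence when participants provide informed consent and continue until the final follow-up questions are completed".

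On clinical records, 13.4 says that "in the event of any AEs and participant withdrawal, the research therapist will review participant clinical notes" and contact clinicians for further information. No other safety review of notes is described. The section headed "13.3 Specification, Timing and Recording of Safety Parameters" is marked N/A. Section 21.1 gives the purposes of record access as confirming the diagnosis and recording participation for the care team, with the participant's consent.

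**The concern.** An event must meet the AE definition before the promise in 13.4.1 to report every AE can apply to it. If the definition counts a crisis referral only during therapy, a referral in the waitlist or follow-up may never become an AE, although it falls inside the reporting window. Two assessors could read the protocol honestly and classify the same event differently.

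The second problem is detection. The notes review described in 13.4 starts from an AE or a withdrawal. A crisis contact that nobody mentions triggers no described check. The same is true of a participant who stops replying without withdrawing.

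The final report will give numbers, types and severity of AEs, and relatedness rests partly on timing. Both need events to be counted by one rule before, during and after therapy. The planned sample is 12 (14.1; the synopsis gives 6-12), so one participant with an unrecorded event is 1/12 = 8.3% of the sample, or 1/6 = 16.7% at the lower figure.

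**Working it through.** **Step 1. Reproduce the plan's own duration.**

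Inputs:
- Waitlist w = 1, 2 or 3 weeks (10.4: "Participants will be randomised to a waitlist time of 1, 2, or 3 weeks").
- Therapy = 3 weeks (8.2: "Three weekly sessions of imagery rescripting will be delivered"; flowchart in 7.3: "Treatment period 3 weeks").
- Follow-up = 2 weeks (11.1: "Participants will continue to complete daily measures about the memory for two weeks").

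Total = w + 3 + 2. The shortest is 1 + 3 + 2 = 6 weeks and the longest 3 + 3 + 2 = 8 weeks. Both match the 6 to 8 weeks stated in 11.1.

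**Step 2. Share of participation time outside therapy** = (w + 2) / (w + 5).

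| Waitlist | Weeks outside therapy | Total weeks | Share |
|---|---|---|---|
| 1 week | 3 | 6 | 50.0% |
| 2 weeks | 4 | 7 | 57.1% |
| 3 weeks | 5 | 8 | 62.5% |

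Assuming 12 participants split 4/4/4, the total is 4 × (6 + 7 + 8) = 84 person-weeks, of which 4 × (3 + 4 + 5) = 48 lie outside therapy: 48/84 = 57.1%.

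The protocol does not define the therapy period for this purpose. If it ran only from the first to the third session (assumed 2 weeks within the same totals), the share would be 4/6 = 66.7% to 6/8 = 75.0%.

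**Step 3. Which events does the limit affect outside therapy?**

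| Event in waitlist or follow-up | AE definition | SAE list | Result |
|---|---|---|---|
| Death, self-harm | No time limit | Listed | Counted |
| Serious violence | No time limit | Listed if police are involved | Counted |
| Complaint about therapy | No time limit | Not listed | Counted |
| Psychiatric admission | Therapy only | Listed, no time limit | Counted as an SAE; texts conflict |
| Crisis referral leading to admission or home treatment team | Therapy only | Listed, no time limit | Counted as an SAE; texts conflict |
| Crisis referral leading to neither, no other item met | Therapy only | Not listed | Ambiguous |

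Only the last row is left without a clear rule. Step 2 gives the time over which that ambiguity applies, not a proportion of events.

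**Step 4. How would such a referral in follow-up week 2 be found?**

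Section 11.1 describes five meetings: two for assessment and three for therapy. The last is at the end of follow-up week 1 and lists the PDS-5, WEMWBS and CSQ-8. Week 2 has daily contact for four memory ratings and no meeting. The notes review needs an AE or a withdrawal first. No described step would find the referral unless the participant or a clinician raised it.

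**The case against.** The strongest reply is that the AE list is open, the SAE list is open and untimed, and 13.4.1 exempts nothing and sets the full window. The serious events are therefore captured throughout. This stands, and it is why the gap comes down to one event type. It does not remove the contradiction, because an explicit time limit on a named event still invites an assessor to leave that event out.

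A grammatical reply is that the limit may attach only to admissions and not to crisis referrals. On that reading crisis referrals are untimed, but the AE definition then restricts admissions, which the SAE list in the same section does not. The texts still need reconciling.

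On detection, the notes review is meant to add information about a known case, and 11.1 and 10.3 provide daily contact, five meetings and close liaison with teams. These are real opportunities to hear of an event. None is described as an adverse event enquiry, however, and the promise of systematic monitoring is not tied to any of them. The absence of a safety row in the flowchart proves little, since the flowchart also omits the daily ratings during treatment that 11.1 requires. Section 13.3 being N/A is likewise only missing detail, since 13.4 carries the safety content.

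A reader might go further and infer that half or more of the reporting period has no safety coverage, or that the waitlist should serve as a comparison rate for harm. The documents support neither. The first confuses calendar time with events and overlooks the SAE list. On the second, 13.4 plans descriptive statistics only, and waitlist exposure would be about 4 × (1 + 2 + 3) = 24 person-weeks under an even split. Nor do the documents say that deterioration would be expected in the two weeks after therapy.

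**Conclusion.** The point holds in a limited form. The therapy-only limit conflicts with the untimed SAE list in 13.4 and with the 13.4.1 window. The event type left ambiguous is a crisis-care referral that leads to neither admission nor home treatment team involvement and meets no other listed item, in the 3 to 5 weeks outside a 3-week therapy phase (50% to 62.5% of participation time). This rests on reading the limit as covering both crisis referrals and admissions, and on the phase lengths in 8.2, 10.4 and 11.1.

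Separately, the only safety review of notes described is triggered by an AE or withdrawal, which is weak support for the monitoring that 13.4 promises. How many events would be missed cannot be estimated from the documents. The change should be made because safety is a stated goal and the correction is small.

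**What to change.** 1. In 13.4, delete the words 'during therapy', so that the 13.4.1 window applies to every AE type.
2. Check the electronic record once for every participant at the end of follow-up week 2, using the same AE list, in addition to the review after an AE or withdrawal.
3. In the final report, state the phase of each event (waitlist, therapy or follow-up) descriptively, without comparing rates.

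The cost is a slightly higher reported event count and one short record check per participant, in a system the researcher already uses. The consent and information documents should also be checked for cover of a routine safety review, since 21.1 gives confirming the diagnosis and recording participation as the purposes of access. If they do not cover it, their wording would need amending.

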#### **13.4.1 Adverse events that do not require reporting**

There are no AEs or SAEs that will not be reported for the case series. The period for reporting will commence when participants provide informed consent and continue until the final follow-up questions are completed.

### **13.5 Stopping Rules**

The trial may be prematurely discontinued by the Sponsor or Chief Investigator on the basis of new safety information or other reasons given by the ethics committee.

## 14. Statistics

Through using a multiple baseline case series design, a waitlist period will control for demand characteristics and effects of time, talking about previous trauma and completing measures. Furthermore, a protocol has been developed for the assessments in order to ensure consistency. Data will not be analysed until all data is collected. Finally, this project will be registered on [clinicaltrials.gov](http://clinicaltrials.gov), ensuring that the method and data-analysis is predetermined.

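### Section 14 does not say which outcomes the waitlist controls: at most the daily ratings. PDS-5 and WEMWBS changes are in practice uncontrolled, and the CSQ-8 has no stated sealed return

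*Combined protocol and SAP*

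**What the plan says.** Section 14 opens by referring to the multiple baseline case series design and then says that "a waitlist period will control for demand characteristics and effects of time, talking about previous trauma and completing measures". It does not say for which outcomes.

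The measures are scheduled as follows (Sections 7.3, 11.1 and 12):

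- **Daily index-memory ratings.** Four 0–100 ratings, listed under the primary parameters in Section 12.1. They are the only row marked in the waitlist column of the flowchart. Section 11.1 says of them: "The research therapist will also be contacting participants every day to answer four questions, either over the phone, by text or email".
- **PDS-5 and WEMWBS.** Secondary. Each is taken at the assessment visit and once more at the appointment one week after treatment. The PDS-5 symptom section is asked about the past week.
- **CSQ-8.** Secondary. It is taken once, at that same post-treatment appointment, where the participant is asked "how satisfied they were with the intervention (Client Satisfaction Questionnaire, CSQ-8").
- **CEQ.** Secondary. It is taken once, at the first therapy session, with a safeguard described twice: "To ensure there are no researcher effects to this measure, participants will rate confidentially and put their answer into an envelope" (Section 11.1) and "To reduce demand characteristics, client forms will be sealed in an envelope upon completion" (Section 12.2).

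One person fills both roles: "participants will meet with the research therapist five times. That includes three times for therapy and twice to answer questions". Section 14.3 lists descriptive statistics, graphs, Tau and reliable change, but does not assign them to measures.

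**The concern.** A waitlist can act as a comparison only for something measured during it. Section 14 names four influences that the waitlist is to control and leaves the outcomes open, so a reader may credit every outcome in the study with that control.

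The protocol's own background shows why this matters. Section 6 faults the earlier rescripting study of traumatic memories for incomplete control of time. It also notes that participants in the control arms of trauma-focused trials in psychosis got better, and that disclosing trauma in a supportive setting may help by itself. A fall in PDS-5 or a rise in WEMWBS could come from any of these. If reliable change is applied to those scales, which Section 14.3 leaves open, improvement could be read as controlled evidence when it is not.

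The CSQ-8 raises a separate question. The waitlist has no bearing on a satisfaction score, which can exist only after therapy. The protection available against pleasing the therapist is the way the form is returned. The protocol specifies that for the CEQ and is silent for the CSQ-8, so satisfaction scores may lean upwards.

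**Working it through.** **Inputs.** Waitlist W = 1, 2 or 3 weeks, randomised (Section 10.4). Treatment 3 weeks and measurement times (Section 7.3). Follow-up 2 weeks (Section 7.2). Four daily questions (Section 11.1). 12 participants (Section 14.1; the Synopsis gives 6–12). I assume that the waitlist starts at the assessment (time 0).

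**1. Check of the phase lengths.** Participation = W + 3 + 2 = 6, 7 or 8 weeks. Section 11.1 says "participation will last a minimum of six and a maximum of eight weeks", so the phase structure reproduces the stated figure.

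**2. Measurements inside the waitlist, per participant.**

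- Daily ratings: 7 × W = 7, 14 or 21 per question. With all four questions that is at most 28, 56 or 84. Section 13.1 allows up to four ratings a day, which I read as the four questions. If only one a day is agreed, the total is 7, 14 or 21.
- PDS-5: 0. WEMWBS: 0. CSQ-8: 0.

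**3. Interval for PDS-5 and WEMWBS.** Assessment to the post-treatment appointment = W + 3 + 1 = 5, 6 or 7 weeks, with no score at the end of the waitlist. The change therefore combines the waitlist, the treatment and one follow-up week. The two PDS-5 recall weeks run from −1 to 0 and from W + 3 to W + 4. Their overlap with the waitlist (0 to W) is 0 weeks for every W.

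**4. Could the randomised waitlist lengths separate time from treatment on these scales?** Take change = τ + β(W + 4), where τ is the treatment effect and β a linear weekly trend, with equal allocation to the three lengths. The least-squares standard error of τ, in SDs of the change score, is √(1/n + m²/S), where m is the mean of W + 4, which is 6, and S is the sum of squared deviations of W.

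- n = 12: S = 8; √(1/12 + 36/8) = 2.14. Unadjusted mean change: √(1/12) = 0.29.
- n = 6: S = 4; √(1/6 + 36/4) = 3.03. Unadjusted: √(1/6) = 0.41.

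The adjusted standard error is 7.4 times the unadjusted one in both cases. Separation is possible in principle but useless in practice, and Section 14.3 plans no such analysis.

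**5. The daily ratings, influence by influence.** Time and repeated measurement operate in the waitlist as they do later, so the comparison has a basis. Demand and talking about trauma are matched only so far as they are the same in each phase. Demand that begins with therapy, and memory work in the sessions, have no equivalent in the waitlist.

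**6. The CSQ-8.** It is completed with 14 − 7 = 7 days of follow-up left, during which the same therapist still solicits up to 7 × 4 = 28 ratings. Section 8.3 says that paper forms carry participant codes only, but not that answers are kept from the therapist.

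**The case against.** The strongest reply is that Section 14 ties its statement to the multiple baseline design, whose logic concerns repeatedly measured outcomes. Here that means the daily ratings, which are among the primary parameters. This is the more natural reading, and it means that the sentence has a real basis. But no section states the limit, and even on this reading the sentence overstates control of demand and of talking about trauma.

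A reader might infer that the protocol plans to attribute PDS-5 or WEMWBS change to the therapy. It does not say so; no analysis is assigned to any measure. Nor is separating time from treatment strictly impossible on those scales, since the randomised intervals differ. It is only far too imprecise.

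A reader might also infer that the CSQ-8 is known to be unprotected, or that the CEQ's rationale carries over in full. Neither is established. Section 14 mentions a separate assessment protocol, which was not available to check and might describe how forms are returned. The CEQ is completed with two rescripting sessions still ahead, whereas the CSQ-8 follows the end of therapy. What stands is that both rate the therapy itself, and that this protocol writes the safeguard down for one and not for the other.

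Two further inferences are weak. Individually agreed prompting differs between people, while the phase comparison is within a person, so it matters only if prompting changes between phases. And the research therapist takes the PDS-5 and WEMWBS on both occasions; what differs by the second is the therapy relationship.

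**Conclusion.** The concern holds in a limited form and is minor. Control of time and repeated measurement can apply at most to the daily ratings. Demand and talking about trauma are addressed there only so far as they stay constant across phases. PDS-5 and WEMWBS have one value before the waitlist, none in it and one after treatment, 5 to 7 weeks apart, so their changes are in practice uncontrolled. The CSQ-8 has no stated confidential return.

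The documents do not allow the direction or size of any bias to be estimated; the counts describe the schedule only. The interval rests on the waitlist starting at assessment and treatment taking three weeks. The 2.14 SD figure rests also on equal allocation and a linear trend. The affected measures are secondary in an exploratory series, and attendance, withdrawals and complaints also inform acceptability. It would go too far to conclude that the waitlist controls nothing or that the primary comparison fails: the daily ratings do have waitlist data.

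**What to change.** 1. **Section 11.1.** Have the CSQ-8 completed confidentially, sealed, and opened only after the final daily rating, with participants told this beforehand. If the separate assessment protocol already provides for this, say so here.

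2. **Section 14.** Replace the statement with, for example:

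> For the daily ratings only, the waitlist provides a comparison for the effects of time and repeated measurement. It addresses demand and talking about trauma only so far as these are constant across phases, and not where they arise in the therapy sessions. PDS-5 and WEMWBS changes from assessment to the 1-week appointment are uncontrolled pre-post changes.

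**Cost.** Up to 12 envelopes, a sentence in Section 11.1 and a short replacement in Section 14. No visit, measure or staff time is added, in keeping with the aim in Section 13.1 of limiting burden. The small downside is that satisfaction scores are seen about a week later; complaints about the therapy are still monitored as adverse events under Section 13.4.
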